3.1.1 Administrative structure of the trial

The trial is sponsored by Boehringer Ingelheim (BI).

A Coordinating Investigator is responsible to coordinate investigators at different centres participating in this multicentre trial. Tasks and responsibilities will be defined in a contract. Relevant documentation on the participating investigators and other important participants, including their curricula vitae, will be filed in ISF.

The trial will be conducted in collaboration with SOGUG a Spanish Cooperative group specialized in the treatment of genitourinary cancers and CNIO the National Center for Oncology investigations in Spain. About 30-35 trial sites in Europe are expected to screen and recruit patients into in this trial. The actual recruitment period is anticipated to be 21 months, i.e. 9 months for stage 1 and 12 months for stage 2. There will not be interruption in

enrolment after completing Cohort A. Therefore by the time of PFS6 and ORR evaluation on the first 25 patients is available, there may be additional patients enrolled into the study.

Biomarker analyses for pre-screening purposes will be performed by a CRO or central lab authorised by BI.

BI has appointed a Trial Clinical Monitor (TCM), responsible for coordinating all required activities, in order to

- manage the trial in accordance with applicable regulations and internal SOPs,
- direct the clinical trial team in the preparation, conduct, and reporting of the trial,
- ensure appropriate training and information of local clinical monitors (CML), Clinical Research Associates (CRAs), and Investigators of participating countries.

Data Management and Statistical Evaluation will be done by BI according to BI SOPs. Safety and efficacy will be continuously monitored by the investigator, and sponsor.

Tasks and functions assigned in order to organise, manage, and evaluate the trial will be defined according to BI SOPs. A list of responsible persons and relevant local information can be found in the ISF.

3.2 DISCUSSION OF TRIAL DESIGN, INCLUDING THE CHOICE OF CONTROL GROUP(S)

This trial will be a single arm open label trial of afatinib monotherapy. No control group will be included as there are no standard treatments available for the patient population investigated.

Patients with metastatic urothelial cancer after failure of, or progression on platinum-containing regimens were selected because they lack treatment options. However, these patients are deemed to benefit from ERBB inhibition if their tumours express ERBB genetic alterations (for details refer to [Sections 2.1](#) and [2.2](#)).

The assignment of patients into 2 separate cohorts is based on observations of anti-tumour activity and biomarker profiles described by Choudhury et al ([P15-03441](#)) for Cohort A and on biomarker profiles demonstrated by Jaegil Kim et al ([R15-6019](#)).

Up to 70 patients will be included into Cohort A using a two stage design which will test the working hypothesis that the true PFS6 rate is >40% at the end of stage 2. The trial will be stopped if $\leq 11/25$ patients at stage 1 show PFS 6 and ≤ 1 patient has a confirmed response.

Cohort B will be exploratory in nature and only include 10 patients.

3.3 SELECTION OF TRIAL POPULATION

Two logs, one for all patients who signed pre-screening consent and one for all patients enrolled into the trial (i.e. who have signed the screening informed consent) will be maintained in the ISF at the investigational site irrespective of whether they have been treated with investigational drug or not.

3.3.1 Main diagnosis for trial entry

Patients to be recruited into this trial must have advanced or metastatic urothelial tract carcinoma that is not amenable to surgical treatment and must have progressed despite previous platinum based chemotherapy. Eligibility for trial participation is also based on positive pre-screening biomarkers – for details refer to [Section 3.1](#). Patients who consent for pre-screening must be willing to provide tumor tissue (including tumour banking) for biomarker analyses (for details refer to [Section 5.5](#)) and storage of 3 x 1mm cores for TMAs. Patients who are eligible to receive treatment on the trial must fulfill the below inclusion criteria (See [Section 3.3.2](#)) and must not meet any exclusion criteria ([Section 3.3.3](#)).

3.3.2 Inclusion criteria

1. Adult patients ≥ 18 years old
2. Patients must have histologically confirmed urothelial tract carcinoma. Patients with urothelial carcinoma of the bladder, upper tract or urethra are eligible.
3. Locally advanced or metastatic urothelial tract carcinoma that is not amenable to surgical treatment.
4. Progressive disease on or after platinum-containing regimen and is not a candidate for another platinum therapy. Following cases will be considered as one line of chemo:
 - Patients receiving platinum-based regimen in the peri-operative setting and subsequently in the metastatic setting
 - Patients who are not refractory to platinum based chemotherapy after one line in metastatic setting (defined as more than 6 months without clinical or radiological PD after the end of first line platinum based chemotherapy) and subsequently receive another line of platinum based chemotherapy in metastatic setting
5. Received no more than one line of prior systemic chemotherapy for recurrent/metastatic disease, and this previous chemotherapy should be platinum based (immunotherapy is not considered as a systemic chemotherapy). If platinum based chemotherapy was administered in the peri-operative setting, patient should have progressed during or within 12 months after treatment .
6. Measurable disease according to RECIST 1.1.
7. ECOG performance status 0 or 1
8. Life expectancy of at least 3 months (12 weeks)
9. Archival tissue biopsies (blocks) available for biomarker testing at pre-screening and for tissue banking for a potential bridging study for CDx (for details refer to [Section 5.5](#)).
10. Patients should complete a pre-screening biomarker analysis and should fulfill the following:
 - Cohort A: Tumour with a ERBB2 or ERBB3 mutation, or ERBB2 gene amplification (for definitions please refer to [section 5.5.1](#))
 - Cohort B: Tumour with EGFR amplification (for definitions please refer to [section 5.5.1](#))
11. Adequate organ function, defined as all of the following:
 - a. Absolute neutrophil count (ANC) $\geq 1500 / \text{mm}^3$.
 - b. Platelet count $\geq 75,000 / \text{mm}^3$.

- c. Estimated creatinine clearance > 45 ml / min. Refer to [Appendix 10.2](#).
 - d. Total Bilirubin ≤ 1.5 times upper limit of (institutional/central) normal (Patients with Gilbert's syndrome total bilirubin must be ≤ 4 times institutional upper limit of normal).
 - e. Aspartate amino transferase (AST) or alanine amino transferase (ALT) \leq three times the upper limit of (institutional/central) normal (ULN) (if related to liver metastases \leq five times ULN).
12. Recovered from any previous therapy related toxicity to \leq Grade 1 at study entry (except for stable sensory neuropathy \leq Grade 2 and alopecia)
 13. Written informed consent for pre-screening that is consistent with ICH-GCP guidelines for tissue, blood, urine collecting and biomarker assessment to confirm eligibility for enrollment into pre-screening phase.
 14. Written informed consent that is consistent with ICH-GCP guidelines to confirm eligibility for enrollment into the trial once pre-screening was successfully completed.

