A recently published trial by Choudhury et al showed that five patients who carried ERBB2/ERBB3 mutations or ERBB2 gene amplifications had a prolonged time to progression/treatment discontinuation of 6.6 months on average compared to the remaining 18 patients in the cohort without ERBB alterations whose disease progressed after only 1.4 months ([P16-03913](#)).

Recently, treatments with checkpoint inhibitors (antiPD1, antiPD-L1) such as Atezolizumab, Pembrolizumab and Nivolumab, have demonstrated benefit in this patient population mainly for those who were PD-L1 positive ([R16-1588](#), [R17-0679](#), [R17-0602](#)).

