3.3.3 Exclusion criteria

1. Chemotherapy within 4 weeks prior to the start of study treatment. Biological therapy or investigational agents within 4 weeks prior to the start of study treatment or prior to passing 5 half-lives (i.e. systemic clearance), whatever comes first.
2. Prior use of EGFR, ERBB2 or ERBB3 targeted treatment
3. Major Surgery within 4 weeks before starting study treatment or planned surgery during the projected course of the study which compromises patient's trial participation by investigator judgement.
4. Radiotherapy within 4 weeks prior to start of study treatment, except palliative radiation to non-target lesions, which may be allowed up to 2 weeks prior to start of study treatment. Tumour lesions situated in a previously irradiated area are usually not considered target lesions unless there has been demonstrated progression in the lesion.
5. Known hypersensitivity to afatinib or its excipients
6. History or presence of clinically relevant cardiovascular abnormalities such as but not limited to uncontrolled hypertension, congestive heart failure NYHA classification of ≥ 3 (Refer to [Appendix 10.6](#)), unstable angina or poorly controlled arrhythmia as by the investigator judgement. Myocardial infarction within 6 months prior to start of study treatment.
7. Any history of or concomitant condition that, in the opinion of the investigator, would compromise the patient's ability to comply with the study or interfere with the evaluation of the efficacy and safety of the test drug
8. Previous or concomitant malignancies at other sites, except effectively treated non-melanoma skin cancers, carcinoma in situ of the cervix, ductal carcinoma in situ, non-invasive urothelial cancer at a different site than the primary tumour or effectively treated malignancy that has been in remission for more than 3 years and is considered to be cured, or incidental localized prostate cancer not requiring treatment

according to investigator's judgement.

9. Requiring treatment with any of the prohibited concomitant medications as described in [Section 4.2.2.1](#) that cannot be stopped for the duration of trial participation
10. Known pre-existing interstitial lung disease or signs and symptoms indicative of the latter as per investigator judgement

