Description of change		Update on the results of previous trials
Rationale for change		To keep protocol updated according to recent publications
Section to be changed		2.2 Trial Objectives
Description of change		Addition of a reference and rewording of parts of the section.
Rationale for change		To add clarity to this section.

Section to be changed		2.3 Benefit-risk assessment
Description of change		Revision of the AEs related to afatinib
Rationale for change		To align the protocol with latest updates on Afatinib and project requirements.
Section to be changed		3.1 Overall trial design and plan
Description of change		Revision of the wording referring to genetic characteristics and conditions for treatment discontinuation
Rationale for change		To keep consistency throughout the trial protocol
Section to be changed		3.1.1 Administrative structure of the trial
Description of change		Increase the number of participating sites
Rationale for change		This is consequence of the expansion of the trial to two additional countries in Europe
Section to be changed		3.2 Discussion of trial design, including the choice of control groups
Description of change		Revision of the text referring to the statistical analysis
Rationale for change		To keep consistency with Section 7.
Section to be changed		3.3.2 Inclusion criteria #4
Description of change		Rewording of the criteria, specifying what could be considered as one line of chemotherapy
Rationale for change		To add clarity to the criteria.
Section to be changed		3.3.2 Inclusion criteria #5
Description of change		Revision of the criteria about previous treatments
Rationale for change		To add clarity to the criteria, especially regarding the use of previous immunotherapy, which was not detailed before.
Section to be changed		3.3.3 Exclusion criteria #4
Description of change		Revision of the wording regarding previous radiotherapy
Rationale for change		To add clarity to the criteria and align to RECIST 1.1
Section to be changed		3.3.3 Exclusion criteria #8
Description of change		Addition of the incidental localized prostate cancer to previous or concomitant allowed malignancies
Rationale for change		To allow for this patients to be entered, since patients with incidental localized prostate cancer

		have good prognostic and would not need further treatment, which would interfere with treatment of urothelial cancer.
Section to be changed		3.3.3 Exclusion criteria #14 and #15

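### Entry requires progression after platinum but not after a later checkpoint inhibitor, so disease control left over from that drug can count as PFS6 success

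*Protocol*

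**What the plan says.** **Progression at entry.** Protocol 3.3.2, inclusion 4, requires "Progressive disease on or after platinum-containing regimen and is not a candidate for another platinum therapy". Section 3.3.1 says that patients "must have progressed despite previous platinum based chemotherapy". The synopsis also ties progression to platinum only.

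**Prior immunotherapy.** Inclusion 5 limits prior chemotherapy to one line for recurrent or metastatic disease and adds that "immunotherapy is not considered as a systemic chemotherapy". The description of Amendment 1 explains that this criterion was revised for clarity, "especially regarding the use of previous immunotherapy, which was not detailed before". Section 1.1 reports that checkpoint inhibitors "have demonstrated benefit in this patient population mainly for those who were PD-L1 positive".

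**Washout.** Exclusion 1 bars "Biological therapy or investigational agents within 4 weeks prior to the start of study treatment or prior to passing 5 half-lives". It glosses five half-lives as systemic clearance and then adds that the earlier of the two limits applies.

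**Other entry criteria that bear on the point.** Inclusion 6 requires "Measurable disease according to RECIST 1.1". Inclusion 12 requires recovery from earlier treatment toxicity, with stated exceptions. Exclusion 7 lets the investigator exclude a patient whose condition would interfere with the efficacy evaluation.

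**Scoring.** Under SAP 7.4 a PFS6 success is a patient alive and progression-free at the 24-week assessment. Assessments after a new anticancer therapy, or more than 30 days after end of treatment, are ignored. SAP 6.3 uses all treated patients for efficacy. Protocol 7.2 tests PFS6 against 40% and ORR against 5%, with Hochberg control at one-sided 0.05. Protocol 7.4 continues to Stage 2 if at least 12 of the first 25 reach PFS6 or at least 2 have a confirmed response.

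**The concern.** Inclusion 4 is satisfied by platinum progression at any earlier time, and immunotherapy may have followed it. The patient of interest progressed on platinum, received a checkpoint inhibitor, stopped it without progressing (for toxicity, for example) and then started afatinib. At trial baseline that disease may be stable or in partial response because of the earlier drug.

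Nothing in the scoring separates that control from an effect of afatinib. Progression under Appendix 10.5 is judged against the smallest lesion sum since trial treatment began, and the SAP's rule on other anticancer therapy looks only forward.

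In a randomised trial such patients would be balanced between arms. Here the only comparison is with a fixed 40%, so each of them raises the count used both at Stage 1 and at the final test. The error would run towards declaring activity.

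**Working it through.** **1. Do the criteria close the gap?**
- Exclusion 1 governs time since the last dose, not disease status. Because the earlier limit applies, a drug whose five half-lives exceed 4 weeks is acceptable at 4 weeks, before the clearance that the same sentence names. The documents give no checkpoint-inhibitor half-life, so this is conditional.
- Inclusion 6 keeps out complete responders, but not stable disease or a partial response with measurable residue.
- Exclusion 7 is general and left to investigator opinion.
- SAP Table 6.2:1, item A2, may flag a patient with more than one earlier systemic line, but a flag does not remove anyone from the treated set.

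The gap remains open.

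**2. Reproduce the plan's figures.** The critical count r is the smallest value with P(X ≥ r | 70, 0.40) ≤ alpha.
- alpha 0.025: r = 37, exact error 0.0199, power at 60% = 0.909.
- alpha 0.05: r = 36, exact error 0.0347, power at 60% = 0.943.
- Also requiring at least 12 of 25 in Stage 1, power is 0.863 and 0.888.

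Table 7.7:1 gives 90.9%, 94.3%, 86.3% and 88.8%. The Stage 1 figures in 7.7 also reproduce: 73% for fewer than 12 of 25 at a 40% rate, and 92% for at least 12 at 60%. The power statement is not in question.

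**3. Which critical count applies?** Under Hochberg, PFS6 is tested at 0.05 only if the ORR p-value is also at or below 0.05; otherwise it is tested at 0.025. For ORR that needs 8 of 70, and P(X ≥ 8 | 70, 0.05) = 0.023. Without an afatinib effect, 37 is therefore the usual threshold and 36 the exception.

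**4. Size of the bias.** Let k of the 70 be patients of the kind described, with PFS6 probability q, and let the other 70 − k have 40%. Neither k nor q is in the documents; both are assumed. The success count is the sum of Bin(k, q) and Bin(70 − k, 0.40), and its mean rises by k(q − 0.40). For k = 7 and q = 0.90 the rise is 7 × 0.50 = 3.5 successes, from 28 to 31.5. Exact convolution, without the Stage 1 rule, gives:

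| k | P(X ≥ 37), q = 50% | q = 60% | q = 80% | q = 90% | P(X ≥ 36), q = 50–90% |
|---|---|---|---|---|---|
| 0 | 2.0% | 2.0% | 2.0% | 2.0% | 3.5% |
| 4 | 2.5% | 3.1% | 4.5% | 5.4% | 4.3–8.7% |
| 7 | 3.0% | 4.2% | 7.9% | 10.4% | 5.0–15.7% |
| 10 | 3.5% | 5.7% | 13.0% | 18.5% | 5.8–26.0% |

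**5. Stage 1.** The same convolution with N = 25 and two such patients raises P(X ≥ 12) from 26.8% to 32–41% for q = 60–90%.

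**6. ORR.** A partial response needs at least a 30% decrease from the trial baseline, which is imaged within 28 days before treatment, and confirmation at least 4 weeks later. Shrinkage already achieved on the earlier drug is inside the baseline, so only further shrinkage counts.

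**The case against.** The strongest reply is that the group is narrow and its size unknown. The immunotherapy must have come after platinum progression and been stopped without progression, because Protocol 4.2.2.1 bars it during study treatment. Measurable disease must remain, earlier toxicity must have settled to the level in inclusion 12, and the investigator must not have used exclusion 7. Section 3.2 describes the intended patients as lacking treatment options. At q = 50% even ten such patients leave the error at 37 of 70 at 3.5%. The protocol also calls its hypotheses exploratory. All of this stands. It limits the size of the problem but does not close the gap.

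A reader might infer more than the documents support:
- *That such patients pass PFS6 whatever afatinib does.* They do not. SAP 7.4 ignores assessments more than 30 days after end of treatment, so success at day 168 means being on afatinib until about day 168 − 30 = 138, near week 20, without progression.
- *That earlier responses open the two-response route to Stage 2.* They are absorbed into the trial baseline, so this route is weak.
- *That the false-positive rate is known to reach 12–26%.* Those values need k of 7–10, q of 80–90% and the 36 threshold, which seldom applies without an afatinib effect.
- *That the SAP plans no analysis by prior immunotherapy.* The public text skips SAP 6.4 and 7.6, so this cannot be judged. A subgroup analysis would not change the primary test in any case.

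**Conclusion.** The eligibility gap is real in the current text, and its direction is clear: it favours success at the PFS6 part of the Stage 1 rule and at the final PFS6 test. Its size cannot be estimated from the documents. With the remaining patients at 40%, N = 70, no Stage 1 adjustment and q between 50% and 90%, the chance of crossing 37 of 70 rises from 2.0% to 2.5–5.4% with four such patients, 3.0–10.4% with seven and 3.5–18.5% with ten. These are assumption ranges, not predictions, and k may be small. The ORR test is little affected. The point deserves a correction because the correction is cheap and the fixed null is the trial's only efficacy comparison; it is no ground for calling the design invalid.

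**What to change.** - **Protocol 3.3.2, inclusion 4:** add a requirement of documented disease progression on or after the most recent prior systemic therapy, including immunotherapy. Align 3.3.1 and the synopsis.
- **SAP:** flag patients already treated who entered without such progression. Add sensitivity analyses of PFS6 and ORR that (a) exclude them and (b) score them as failures. Label (b) as a worst-case bound, since it is biased in the opposite direction; (a) is the neutral comparison.
- **Protocol 3.3.3, exclusion 1:** reconcile the two parts of "prior to passing 5 half-lives (i.e. systemic clearance), whatever comes first", because taking the earlier limit can fall short of the clearance named in the same phrase. The sponsor must decide which meaning was intended.

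The cost is one eligibility clause, a record of disease status after the last prior therapy, one extra table, and the loss of a small number of otherwise eligible patients.

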3.3.3 Exclusion criteria

1. Chemotherapy within 4 weeks prior to the start of study treatment. Biological therapy or investigational agents within 4 weeks prior to the start of study treatment or prior to passing 5 half-lives (i.e. systemic clearance), whatever comes first.
2. Prior use of EGFR, ERBB2 or ERBB3 targeted treatment
3. Major Surgery within 4 weeks before starting study treatment or planned surgery during the projected course of the study which compromises patient's trial participation by investigator judgement.
4. Radiotherapy within 4 weeks prior to start of study treatment, except palliative radiation to non-target lesions, which may be allowed up to 2 weeks prior to start of study treatment. Tumour lesions situated in a previously irradiated area are usually not considered target lesions unless there has been demonstrated progression in the lesion.
5. Known hypersensitivity to afatinib or its excipients
6. History or presence of clinically relevant cardiovascular abnormalities such as but not limited to uncontrolled hypertension, congestive heart failure NYHA classification of ≥ 3 (Refer to [Appendix 10.6](#)), unstable angina or poorly controlled arrhythmia as by the investigator judgement. Myocardial infarction within 6 months prior to start of study treatment.
7. Any history of or concomitant condition that, in the opinion of the investigator, would compromise the patient's ability to comply with the study or interfere with the evaluation of the efficacy and safety of the test drug
8. Previous or concomitant malignancies at other sites, except effectively treated non-melanoma skin cancers, carcinoma in situ of the cervix, ductal carcinoma in situ, non-invasive urothelial cancer at a different site than the primary tumour or effectively treated malignancy that has been in remission for more than 3 years and is considered to be cured, or incidental localized prostate cancer not requiring treatment

according to investigator's judgement.

9. Requiring treatment with any of the prohibited concomitant medications as described in [Section 4.2.2.1](#) that cannot be stopped for the duration of trial participation
10. Known pre-existing interstitial lung disease or signs and symptoms indicative of the latter as per investigator judgement
11. Any history or presence of poorly controlled gastrointestinal disorders that could affect the intake/absorption of the study drug (e.g. Crohn's disease, ulcerative colitis, chronic diarrhoea, malabsorption) as per investigator judgement
12. Active hepatitis B infection (defined as presence of HepB sAg and/ or Hep B DNA), active hepatitis C infection (defined as presence of Hep C RNA) and/or known HIV carrier.
13. Known brain metastases or signs hereof, uncontrolled spinal cord compression or leptomeningeal carcinomatosis
14. Female patients who are nursing or are pregnant or are planning to become pregnant on this trial
15. Women of child-bearing potential (WOCBP) and men who are able to father a child, unwilling to be abstinent or use highly effective methods of birth control that result in a low failure rate of less than 1% per year when used consistently and correctly prior to study entry*, for the duration of study participation and for at least 2 weeks after treatment has ended. Patients will be considered to be of childbearing potential unless surgically permanently sterilized (e.g. hysterectomy, bilateral oophorectomy, bilateral salpingectomy), or post-menopausal for at least 12 months without an alternative medical cause.

*A list of contraception methods meeting these criteria is provided in the patient information sheet, and [Section 4.2.2.3](#).

